Urinary Tract Dilations in Prenatal and Postnatal Life

ID: 0292/21/2023-00590

[name] [name], PhD.

19.12.2023

Study protocol

Brief Title

Urinary Tract Dilations in Prenatal and Postnatal Life

Director of study and central contact person

[name] [name], PhD.

Main sponsor

SonoClinic, s.r.o, [name]

Workplaces collaborating on the project

Emporia, s.r.o., [name]

NefroSa s.r.o., [name]

Solvers

[name] [name], PhD.

[name]. [name]., MPH

[name]

Scientific goals of the study

1. Multidisciplinary survey on awareness, state of diagnosis and management of patients with dilatation of the urinary tract.
2. The primary goal is the prediction of severe postnatal course and surgical intervention in fetuses with dilatation of the urinary tract according to the UTD classification from 2014.
3. The secondary goal is the creation of a model proposal for prenatal and postnatal care of a patient with dilatation of the urinary tract.

Duration of the study

Study start: january 2023

Study completion: june 2026

Introduction

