Despite the obvious advantages, the UTD classification is generally not often used in clinical practice. It is most commonly used by pediatric radiologists. Only 19% of pediatric urologists use this system compared to 70% of those who use the SFU scoring system despite UTD showing higher reliability (Gray, 2022). Also, a literature review between 2017 and 2019 confirmed that only 6% of studies use the UTD classification system, while 37% use the SFU grading system and 33% use the APRPD system. Interestingly, approximately 20% of studies do not use any scoring system when describing urinary tract dilations in children (Suson, 2020). While the authors, members of pediatric radiology, created a computer application as a training aid for teaching the UTD classification system, which can be shared and used at any time (Maizels, 2017).

There are several reasons for the less-than-expected use of the UTD classification system. Complexity described by some departments, lack of information between departments, as the system was created for multidisciplinary cooperation, incompleteness (classification is always based on the presence of intrarenal dilation, does not take into account isolated dilatations of the ureter or other anomalies of the urinary tract, which is gradually being modified), impossibility to predict some dilatational anomalies of the urinary tract, such as vesicoureteral reflux, as well as national or international standards that have not yet been developed in many countries (Nguyen 2022).

The UTD classification system proposes a unified evaluation system for prenatal and postnatal dilative diseases of the urinary tract. A review of available studies and literature showed that the system can predict the clinical consequences of the disease and has better inter- and intraobserver reliability compared to other systems. The goal is to increase awareness of this system among specialties and create standardized management plans for the patient with dilated urinary tract disease (Green 2022, Nguyen 2022).

Methodology of study

Multidisciplinary survey on awareness

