The study will also include a multidisciplinary survey of awareness regarding the issue of urinary tract dilation diseases. Specialists from the fields of pediatrics, neonatology, pediatric nephrology, pediatric nephrology, gynecology, ultrasound in gynecology and obstetrics, or radiology will be approached by filling in a short questionnaire created via docs.google.com, in which we will find out information about the methods used for prenatal and postnatal diagnosis of dilations urinary tract, the method of classifying these anomalies and their subsequent solution.

Questionnaire for gynecologists, prenatal sonographers:

1. Do you encounter dilation of the urinary tract in fetuses in your practice?
 - a) Yes, often.
 - b) Sporadic.
 - c) Rarely, almost never.
2. In case of US finding of dilation of the urinary tract in the second or third trimester:
 - a) I will only describe the given anomaly descriptively.
 - b) I will classify the anomaly in the classification system.
3. When describing the anomaly, do you use terms such as "pyelectasis, pelviectasis, hydronephrosis"?
 - a) Yes.
 - b) No.
4. If you use a classification in the evaluation of dilations of the urinary tract, which one?
 - a) SFU classification system (Society for Fetal Urology Grading system).
 - b) UTD (Urinary Tract Dilation) classification system.
 - c) I don't use any.
5. If dilatation of the urinary tract is found in the third trimester, do you recommend a pregnant woman to be checked by a pediatric nephrologist after birth?
 - a) Yes.
 - b) No.
 - c) I will instruct her to mention the finding as part of the newborn USG screening.
6. Are you informed about the postnatal finding in a child with prenatally diagnosed dilation of the urinary tract?
 - a) Yes, I will ask the pregnant woman to inform me about the child's examinations.
 - b) Yes, I work with a pediatric nephrologist who sends me the findings.
 - c) No, it is not in my interest.

7. Do you think that the system of care for a patient (fetus, child) with dilatation of the urinary tract is sufficient in our country?

a) After the prenatal diagnosis of dilation of the urinary tract, I do not deal with the management of the fetus and the child.

b) It is not sufficient, there are no standards in prenatal care for a fetus with dilation of the urinary tract.

c) The current management system for excretory system anomalies and dilatations is sufficient.

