8. Have you encountered or do you use the prenatal UTD classification system (2014) when evaluating dilations of the urinary tract?

a) Yes.

b) No.

9. Do you think that the UTD classification system is optimal for prenatal and postnatal management of a patient with urinary tract dilatation?

a) Yes, it is usable in practice in risk stratification in fetuses with UTD.

b) No, it is too complex and does not cover all dilative diseases of the urinary tract.

c) I can't comment on that.

10. What are the normal values of renal pelvis width (APRPD) in the second, third trimester and postnatally?

a) 4-7 mm, 7-10 mm, over 10 mm

b) Up to 4 mm, 4-7 mm, 10 mm

c) 4-5 mm, 7-8 mm, 10 mm

Questionnaire for pediatricians, neonatologists, pediatric urologists and nephrologists, radiologists:

1. In your practice, do you encounter a patient with dilation of the urinary tract?

a) Yes, often.

b) Sporadic.

c) Rarely, almost never.

2. In case of US finding of dilation of the urinary tract in a child:

a) I will only describe the given anomaly descriptively.

b) I will classify the anomaly in the classification system.

3. When describing the anomaly, do you use terms such as "pyelectasis, pelviectasis, hydronephrosis"?

a) Yes.

b) No.

4. If you use a classification system when evaluating urinary tract dilations, which one?

a) SFU classification system (Society for Fetal Urology Grading system).

b) UTD (Urinary Tract Dilation) classification system.

b) I don't use any.

5. When examining a child with dilatation of the urinary tract, are you interested in prenatal findings?

a) Yes, I am interested in the finding and its severity in the prenatal period.

b) It is not useful information for me

c) Sometimes I ask the patient about it, or she reports it to me herself.

6. Have you encountered or are you using the postnatal UTD classification system (2014) when evaluating dilations of the urinary tract?

a) Yes.

b) No.

7. Do you think that the UTD classification system is suitable for the prenatal and postnatal management of a patient with urinary tract dilation?

d) Yes, it is applicable in practice in risk stratification in a patient with UTD.

e) No, it is too complex and does not cover all dilative diseases of the urinary tract.

f) I can't comment on that.

8. Do you think that the system of care for a patient (fetus, child) with dilatation of the urinary tract is sufficient in our country?

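### As printed, neither survey form records the respondent's specialty, so answers cannot be broken down within a form, chiefly among the five disciplines pooled on the postnatal form

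*Protocol*

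**What the plan says.** Goal 1 under Scientific goals of the study is a "Multidisciplinary survey on awareness, state of diagnosis and management of patients with dilatation of the urinary tract". Goal 3 is a proposed model of prenatal and postnatal care, which the Introduction describes as a model for multidisciplinary cooperation.

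The Methodology section prints two forms. The first is headed "Questionnaire for gynecologists, prenatal sonographers" and has 10 items. The second is headed "Questionnaire for pediatricians, neonatologists, pediatric urologists and nephrologists, radiologists" and has 9. On who is invited, the protocol says: "Specialists from the fields of pediatrics, neonatology, pediatric nephrology, pediatric nephrology, gynecology, ultrasound in gynecology and obstetrics, or radiology will be approached". The same list stands under Focus of the study. It names pediatric nephrology twice and does not name pediatric urology.

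The postnatal form opens with "In your practice, do you encounter a patient with dilation of the urinary tract", and no background item comes before it. Its familiarity item asks "Have you encountered or are you using the postnatal UTD classification system (2014) when evaluating dilations of the urinary tract".

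The Review of the literature says that the UTD classification is used most by pediatric radiologists. It continues: "Only 19% of pediatric urologists use this system compared to 70% of those who use the SFU scoring system". It closes with "The goal is to increase awareness of this system among specialties".

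**The concern.** The postnatal form puts five disciplines into one unlabelled pool. Two of them, urologists and radiologists, are close to the groups that the literature review contrasts. If use of the classification differs between disciplines, a pooled percentage reflects who replied as well as what each discipline does. A reader of the results could not see which specialty lacks awareness, could not reweight the answers to a known composition, and could not set the urologists' answers beside the 19% that the protocol cites. The prenatal form has the same limit on a smaller scale, since it pools general gynecologists with prenatal sonographers.

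This is not detail that a protocol may leave to an analysis plan. An analysis plan can define tables, but it cannot tabulate by a variable that the printed instrument does not collect.

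**Working it through.** **Step 1: look for a specialty field.** I read every printed item and the Demographics paragraph.

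| Place | Items | Items recording the respondent's specialty |
|---|---|---|
| Prenatal form | 10 | 0 |
| Postnatal form | 9 | 0 |
| Both forms | 19 | 0 |

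Some items mention other specialists (prenatal items 5 and 6, postnatal item 9). They ask about referral, feedback and cooperation, not about the respondent. The Demographics paragraph covers the pregnancy, the fetus and the family. On delivery, the protocol says only that specialists will be approached with a short online form. It describes no separate link per specialty and does not say whether replies are anonymous.

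**Step 2: what the design keeps.** Item 4 on both forms asks which classification is used. Familiarity with the UTD system is asked in prenatal item 8 and postnatal item 6. The comparison of prenatal with postnatal specialists is therefore available. The breakdown within each form is not: two groups on the prenatal form, five on the postnatal form.

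**Step 3: why a pooled figure is ambiguous.** Assume five equally sized groups and a pooled 40% answering yes to postnatal item 6.

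- 40% in every discipline: (5 × 40) / 5 = 40%.
- 100% in two disciplines and 0% in three: (2 × 100 + 3 × 0) / 5 = 40%.

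The pooled answers cannot separate these two situations, which would call for different action.

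**Step 4: dependence on the mix, as a range.** The protocol gives no sample size for the survey and no figure for radiologists, so this step only illustrates. Inputs: 19% use in pediatric urologists (Review of the literature); an assumed rate r in radiologists; an assumed form answered by these two groups only, in proportions 80:20 or 20:80.

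- Pooled at 80:20 = 0.8 × 19 + 0.2 × r
- Pooled at 20:80 = 0.2 × 19 + 0.8 × r
- Difference = 0.6 × (r − 19)

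| Assumed r | Pooled at 80:20 | Pooled at 20:80 | Difference |
|---|---|---|---|
| 19% | 19.0% | 19.0% | 0.0 points |
| 40% | 23.2% | 35.8% | 12.6 points |
| 60% | 27.2% | 51.8% | 24.6 points |
| 80% | 31.2% | 67.8% | 36.6 points |

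The difference vanishes if the disciplines do not differ and grows with the gap between them. No single row is an estimate for this survey.

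**Step 5: which item could be compared with 19%.** That figure concerns use. Postnatal item 6 accepts either having met the system or using it, so it measures familiarity. Only item 4 could be set against the 19%, and only if the specialty is known.

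**The case against.** The strongest reply is that the protocol never promises a comparison by specialty. Goal 1 and the Methodology section describe a survey of the methods, classification and management in use. The remarks about differences between disciplines, and about raising awareness among specialties, belong to a cited literature review and not to the study's objectives. This stands. A reader might infer that the survey fails an aim it has set itself. The documents do not support that, because the need for a breakdown is inferred from the word multidisciplinary and from the care model the study is meant to produce.

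Other parts of the reply also stand:

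- A reader might infer that all answers end in one pooled percentage. They do not, because the two forms keep the prenatal and postnatal sides apart.
- A reader might infer that the loss cannot be repaired once answers are in. The protocol is silent on separate mailings or identifiable replies. Silence shows that no link is described, not that none could exist.
- A reader might take the repeated nephrology entry to mean that urologists will not be approached. The postnatal form's heading and its item 9 both name them, so a wording slip is the likelier explanation.
- The survey is a descriptive component, and the primary goal does not depend on it.

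The reply leaves the central fact untouched: as printed, the forms do not record the one variable needed to break the answers down by discipline.

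**Conclusion.** The point holds in a limited form. From the printed forms alone, answers cannot be broken down or reweighted by discipline within a form, and the protocol describes no other route. The loss falls mainly on the five disciplines of the postnatal form. It reduces what goal 1 can contribute to the care model, but it contradicts no stated objective and leaves the cohort study as it is.

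Its size in percentage points is unknown. The 13 to 37 points above rest on assumed radiologist rates of 40% to 80%, on assumed mixes, and on two disciplines out of five. They show that the mix can matter, not how much it will. This is a worthwhile improvement at very low cost, not a fault that invalidates the survey.

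**What to change.** 1. Add one compulsory item, *Your specialty*, at the start of each online form. Postnatal form: pediatrics, neonatology, pediatric nephrology, pediatric urology, radiology. Prenatal form: general gynecology or prenatal ultrasound.
2. Report the answers by that item. Use item 4 on both forms for use of the UTD classification, and prenatal item 8 and postnatal item 6 for familiarity. Compare only item 4 with the 19% for pediatric urologists.
3. Bring the invitation lists, under Focus of the study and in the Methodology section, into line with the postnatal form's heading, so that pediatric urology is named and pediatric nephrology appears once.
4. If the survey has already closed, report results by form only and state that they cannot be broken down by specialty, unless separate mailings or similar records allow it.

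The cost is one multiple-choice item per form and a slightly longer questionnaire. Some specialties may have few respondents, so their percentages should be shown with their denominators.

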The selected specialist (sonographer, soler) is the fetus examined by ultrasound in the third trimester after the 28th week, optimally after the 32nd week of pregnancy. The urinary tract of the fetus is examined again according to the recommendation of the UTD classification system, all 7 parameters and the amount of amniotic fluid are assessed again. Re-classification or re-evaluation of the finding and carried out risk stratification according to the severity of the finding. Fetuses with normal findings are not recommended for further follow-up, fetuses with UTD A1 are recommended for a postnatal control by a pediatric nephrologist within a month after birth. Fetuses with a high risk of persistence or progression of the finding, i.e. UTD A2-3, are recommended for ultrasound control in 4-6 weeks, and then according to the findings, prenatal consultation with a pediatric nephrologist is recommended, with whom postnatal management will be discussed and postnatal controls will be optimized. The aim of

the evaluation of findings will be to predict the risk of postnatal surgical intervention in the child in the case of serious prenatal findings.

The fourth part of the study – management of a child with UTD by a pediatric nephrologist:

According to the stratification of the risk of UTD pathology of the urinary tract in the child, an examination by a specialist is established, where the initial examination is carried out within a month of the child's age (individually according to the findings). Subsequently, the ultrasound finding on the urinary system is reevaluated according to the UTD classification to UTD P1-P3 (table 3) with the assignment of the corresponding risk (low, intermediate, high, table 4 and 5) and the child is adequately managed according to the recommendations and condition (conservative management, VCUG, cystoscopy, surgical procedure, antibiotic prophylaxis and the like). The child is followed in the study until the age of 6 months.

All case findings are recorded on prepared media (USB), archived (external hard disks) and described according to the recommendations of the 2014 UTD classification system.

The obtained results will be subjected to statistical analysis. A multidisciplinary management plan for a patient with urinary tract dilatation will be created. All results and conclusions will be subsequently published.

Literature

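### Item 2 of both survey forms has no answer for respondents who do not perform or report the ultrasound, so its classification share is distorted in an unknown direction

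*Protocol*

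**What the plan says.** The survey is the first scientific goal. The protocol's section on the multidisciplinary survey names among its targets "the method of classifying these anomalies and their subsequent solution".

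There are two forms. One is for gynecologists and prenatal sonographers. The other is headed "Questionnaire for pediatricians, neonatologists, pediatric urologists and nephrologists, radiologists". Item 2 of the second form opens "In case of US finding of dilation of the urinary tract in a child" and gives two answers:

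- (a) "I will only describe the given anomaly descriptively"
- (b) "I will classify the anomaly in the classification system"

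Item 2 of the prenatal form asks about a second- or third-trimester finding and offers the same two answers.

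Item 4 of the postnatal form asks separately "If you use a classification system when evaluating urinary tract dilations, which one", with SFU, UTD and none as answers. Some other items do have an opt-out: item 7 of the postnatal form allows "I can't comment on that", and item 9 has a similar answer.

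On analysis, the protocol says only "The obtained results will be subjected to statistical analysis". It gives no scoring rule, denominator or mandatory-answer rule for the survey.

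**The concern.** Both answers to item 2 are in the first person and read most naturally as addressed to whoever writes up the scan. The forms reach a wider group. A pediatrician or neonatologist who works from a radiologist's report has no answer that fits, and the same holds for a gynecologist who does not scan.

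The protocol itself separates these roles. In the literature review, Recommendation 2 of the UTD system describes a report passing to the doctor who will handle the finding after birth. The survey section lists gynecology apart from ultrasound in gynecology and obstetrics. Neither passage says how many respondents are on each side.

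At stake is how the item 2 share can be read. A given percentage may reflect scanners who choose not to classify, or respondents who do not scan at all. The first would call for training in the UTD system, the second would not. The care model is to be built after the survey, so the distinction has some practical use.

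**Working it through.** The protocol states no expected classification rate, sample size or precision for the survey, so there is no figure to reproduce. The check has two parts.

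**1. Can the groups be separated from what is collected?** None of the ten prenatal or nine postnatal items asks whether the respondent performs or reports ultrasound. None asks specialty either, and specialty would not be enough, since one specialty can contain both roles. The none answer in item 4 also merges the two groups. No later choice of denominator, including one in a statistical analysis plan, can restrict item 2 to those who scan, because that fact is not recorded.

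**2. Which way does the share move?** Define:

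- s = share of item 2 respondents who do not perform or report scans
- p = share choosing (b) among those who do
- q = share choosing (b) among those who do not

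Observed share = (1 − s)p + sq, so bias = s(q − p).

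All three values are assumptions. With p = 0.40 and s = 0.30:

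| How non-scanners answer | Observed share | Bias |
|---|---|---|
| All choose (a), q = 0 | 0.70 × 0.40 + 0.30 × 0 = 0.28 | −12 points |
| Same rate as scanners, q = 0.40 | 0.28 + 0.12 = 0.40 | 0 |
| q = 0.50 | 0.28 + 0.15 = 0.43 | +3 points |
| All choose (b), q = 1 | 0.28 + 0.30 = 0.58 | +18 points |
| All skip the item | 0.40 | 0 |

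Over p from 20% to 60% and s from 10% to 50%, the extremes are:

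- q = 0: bias = −sp, from −0.10 × 0.20 = −2 points to −0.50 × 0.60 = −30 points
- q = 1: bias = s(1 − p), from 0.10 × 0.40 = +4 points to 0.50 × 0.80 = +40 points

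Read in reverse, an observed 28% fits p = 40% (s = 30%, q = 0), p = 28% (any s, q = p) or p = 20% (s = 10%, q = 1: 0.90 × 0.20 + 0.10 = 0.28). The forms collect nothing that would choose among these.

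**The case against.** A reader might infer that non-scanners will be counted as non-classifiers and that the rate is therefore understated. If the true rate were 50% and 30% to 60% of respondents did not scan, the form would show 0.50 × 0.70 = 35% down to 0.50 × 0.40 = 20%. The documents do not support this. The figures hold only if every non-scanner chooses (a), and the protocol neither says how such respondents will answer or be scored nor whether they may skip the item. Understatement requires q < p, and nothing is known about q.

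The defense goes further. The stem does not say that the respondent holds the probe. Recommendation 2 has images accompany the report, so a receiving clinician could grade the finding. The literature review reports use of the systems by pediatric urologists without limiting it to those who scan. On that view, some receivers who choose (a) are true non-classifiers. This stands, and it is a further reason to leave the direction open. It does not remove the ambiguity, because such a person still cannot be told apart from a scanner who does not classify.

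It is also fair that item 4 and the direct question on UTD use (item 6 postnatal, item 8 prenatal) partly guard against reading a low item 2 share as ignorance of the system. A non-scanner can answer these validly, so item 4 should not be restricted to those who scan. Finally, the protocol does not say which pediatricians, neonatologists or gynecologists do not scan, so s could be small.

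**Conclusion.** The point holds as a defect of the printed questionnaire. Item 2 on both forms forces a two-way choice that does not fit a respondent who only receives reports, and no item identifies such respondents. The resulting share is biased by s(q − p), with sign and size unknown. It vanishes if s is zero, if q equals p, or if non-scanners leave the item blank. The ranges shown rest wholly on assumed values and illustrate sensitivity; they do not estimate the error in this survey.

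The weight is minor. Item 2 is one descriptive item under goal 1. No hypothesis or sample size depends on it, and the primary goal of predicting a severe postnatal course and surgery is unaffected.

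**What to change.** - Add to item 2 on both forms a third answer: *I do not perform or report the ultrasound myself*.
- Report items 2 and 3 among respondents who perform or report the scan.
- Keep item 4 for all respondents, shown separately for those who scan and those who receive reports. A receiver who grades from the report or its images is then still captured there.
- Flag any answers collected before the option was added. The protocol is dated December 2023 and gives a study start of January 2023, so some may already exist. Tabulate them separately for item 2.

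The cost is one answer option in each online form, a stated denominator, and a smaller base for items 2 and 3. Answers already collected cannot be reassigned unless those respondents are asked again.

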Review of the literature

Dilative diseases of the urinary tract are the most frequent findings during prenatal ultrasound examination of the fetus. We detect them in approximately 1-2% of fetuses examined during pregnancy (Nguyen 2014). Although in 50-70% of cases they are a physiological or transient finding, they can be a sign of a wide spectrum of anomalies of the urinary tract. These include uteropelvic junction obstruction (10-30%), vesicoureteral reflux (10-40%), ureterovesical junction obstruction (5-15%), multicystic renal dysplasia (2-5%) and posterior urethral valve (1-5%). Less frequent causes are ectopic ureter and the presence of a ureterocele in a double outlet system, polycystic kidney disease. Prenatal identification of the above-mentioned urinary tract anomalies is extremely important in order to prevent the development of possible complications (urinary tract infection, kidney stones, kidney failure) and to enable the creation of adequate, precisely targeted postnatal management of the detected anomaly (Nguyen 2010).

In common clinical practice, for many years, there was a lack of correlation between prenatal and postnatal ultrasound findings of urinary tract dilatation diseases with inconsistency in the description and classification of the degree of severity, which ultimately affected the clinical assessment and treatment planning (Mileto 2018). For this reason, the Urinary Tract Dilation Classification System (UTD Classification System) was created in 2014 in the city of Lithicum in the United States. It was compiled by representatives of eight major scientific societies: the American College of Radiology (ACR), the American Institute of Ultrasound in Medicine (AIUM), the American Society of Pediatric Nephrology (ASPN), the Society for Fetal Urology (SFU), the Society for Maternal-Fetal Medicine (SMFM), the Society for Pediatric Urology (SPU), the Society for Pediatric Radiology (SPR), and the Society of Radiologists in Ultrasounds (SRU), (Nguyen 2014, Mileto 2018). Their meeting had a two goals: to propose a unified description of urinary tract dilatation diseases prenatally and postnatally and to create a standardized framework for prenatal evaluation of isolated urinary tract dilatation based on USG findings, which can be applied in the postnatal period (Nguyen 2014, Mileto 2018).

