a) It is not sufficient, the standards in prenatal and postnatal care of a patient with dilation of the urinary tract are insufficient.

b) The current management system for excretory system anomalies and dilatations is sufficient.

9. Would we welcome greater cooperation between specialists (gynecologist, neonatologist, pediatrician, pediatric urologist, pediatric nephrologist) in the diagnosis and treatment of a patient (fetus, child) with dilation of the urinary tract?

a) Yes, it is necessary.

b) No, as it is now, it is sufficient.

c) I can't judge it.

Study

Inclusion criteria of cases in the study:

1. Singleton pregnant women whose fetuses were diagnosed with dilation of the urinary tract as an isolated US finding before the 28th week of pregnancy. Dilation of the urinary tract was categorized according to the 2014 UTD classification system.
2. Fetal patients with subsequent US control in the third trimester after the 28th week of pregnancy.
3. Newborns and children with prenatally diagnosed UTD, which, depending on the severity, required a postnatal examination by a pediatric nephrologist within a month after birth and then in his follow-up up to 6 months after birth.

Exclusion criteria:

Multiple pregnancies, UTD diagnosed only in the third trimester, associated anomalies of other organs, aneuploidy, newborns and children monitored by someone other than a selected pediatric nephrologist, patients who were lost from follow-up (did not come for recommended control, etc.).

Study population:

Approximately 4,000 morphological ultrasound examinations of fetuses are performed annually at the SonoClinic and Emporia workplaces. Approximately 60-80 cases of dilation of the urinary tract are detected annually. In 80% of them there is a complete adjustment before delivery, the remaining approximately 20% have persistent dilation of the urinary tract with varying degrees of severity (UTD A1 – low risk, UTD 2-3 – high risk). According to the recommendations of the UTD classification, these fetuses are subsequently recommended for postnatal examination by a pediatric nephrologist. The estimated number of cases with dilation of the urinary tract for analysis postnatally will be 180 to 230.

Demographics:

Age, parity, occurrence of urinary tract anomalies in the child's father and siblings, sex of the fetus, method of conception.

Study design:

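### Inclusion item 2 and the loss-to-follow-up exclusion make eligibility depend on events after the second-trimester UTD class, and terminations, deaths and births before the control scan are not recorded

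*Protocol*

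**What the plan says.** The primary goal (Protocol, *Scientific goals of the study*, goal 2) is to predict severe postnatal course and surgical intervention in fetuses with urinary tract dilation. The first class is assigned in the second trimester (*Study design*, second part).

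The list under *Inclusion criteria of cases in the study* has three items:

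- Item 1 sets the index population: "Singleton pregnant women whose fetuses were diagnosed with dilation of the urinary tract as an isolated US finding before the 28th week of pregnancy".
- Item 2 reads "Fetal patients with subsequent US control in the third trimester after the 28th week of pregnancy". The third part of *Study design* describes the same scan as "examined by ultrasound in the third trimester after the 28th week, optimally after the 32nd week of pregnancy".
- Item 3 covers newborns and children "which, depending on the severity, required a postnatal examination by a pediatric nephrologist within a month after birth", with follow-up to 6 months.

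The *Exclusion criteria* remove multiple pregnancies, dilation first seen in the third trimester, anomalies of other organs and aneuploidy. They also remove "newborns and children monitored by someone other than a selected pediatric nephrologist" and "patients who were lost from follow-up (did not come for recommended control, etc".

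Termination, fetal death, neonatal death and birth before the control scan are not mentioned anywhere. The items listed under *Demographics* include no pregnancy outcome. Severe postnatal course is not defined.

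**The concern.** A prediction made from a class assigned before week 28 should be judged on everyone who received that class. Here a case counts only if the pregnancy continues to a later scan and the patient is not lost afterwards. Some of the events that stop a case from qualifying may themselves be serious consequences of urinary tract disease. Others, such as birth before the control scan, leave a living child who may still be operated on.

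The study is meant to yield a care model, and counselling would start from the prenatal class. A risk that describes only the fetuses reaching the later examinations does not describe the population being counselled. This cannot be left to an analysis plan, because outcomes that were never recorded cannot be recovered at the analysis stage.

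**Working it through.** **1. Which cases can qualify.** Every row starts from a singleton fetus with isolated dilation and a UTD class before week 28, so item 1 is met.

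| Event after the class is assigned | Item 2 (control scan) | Postnatal stage | Provision in the protocol |
|---|---|---|---|
| Termination or fetal death before the control scan | cannot be met | not reached | none |
| Birth before any control scan | cannot be met | can still be reached; surgery possible | none |
| Neonatal death before the nephrologist visit | may be met | may not be reached | none |
| Missed control | not met | excluded as lost | removed, not counted |

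The open-ended wording of the loss exclusion does not separate a missed visit from a death, a termination or an early birth.

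**2. The plan's own numbers.** *Study population* gives 60-80 detected cases a year, about 20% of them persistent. The study runs from January 2023 to June 2026, which is 3.5 years.

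- Detected: 60 x 3.5 = 210 to 80 x 3.5 = 280.
- Persistent: 0.20 x 210 = 42 to 0.20 x 280 = 56.

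The stated 180-230 cases for postnatal analysis does not follow from the persistent cases. It lies nearer to all cases detected over 3 years (180-240). That mismatch is a separate matter. What matters here is that the protocol gives no loss rate and states no allowance for loss.

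**3. Direction of the bias.** Let s be the event rate among kept cases, L the share of fetuses in a class that is lost, and d the share of lost cases that had the event.

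Rate per fetus identified = s(1 - L) + dL = s + L(d - s).

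The kept-only rate s is therefore too low when d exceeds s and too high when d is below s. All three quantities are assumptions, since the documents give none of them. With s = 30%:

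| L | Every loss counts as an event (d = 1) | No lost case has the event (d = 0) |
|---|---|---|
| 5% | 0.30 x 0.95 + 0.05 = 33.5% | 0.30 x 0.95 = 28.5% |
| 10% | 0.30 x 0.90 + 0.10 = 37.0% | 0.30 x 0.90 = 27.0% |
| 20% | 0.30 x 0.80 + 0.20 = 44.0% | 0.30 x 0.80 = 24.0% |

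Over s = 20-40% and L = 5-20%, the range is:

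- for d = 1: from 0.20 x 0.95 + 0.05 = 24% to 0.40 x 0.80 + 0.20 = 52%;
- for d = 0: from 0.20 x 0.80 = 16% to 0.40 x 0.95 = 38%.

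The d = 1 column is the extreme in which every loss is counted as severe course. The d = 0 column is surgery alone when no lost fetus had surgery. Children born before the control scan and later operated on raise d above zero for surgery too, so they are lost surgery events under either definition.

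**The case against.** **The items may be stages.** They name different subjects (pregnant women, fetal patients, children) and follow the parts of the study design, so they need not all apply to each case. Item 3 applies only according to severity. If it bound everyone, the roughly 80% of fetuses that resolve, and are then not followed further, would be ineligible as well. This stands as far as it goes: a reader might infer that every case must reach a nephrologist visit, and the text does not say so. But the staged reading does not bring the lost cases back. The loss exclusion still applies, and no stage records termination, death or early birth.

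**Downward bias.** A reader might infer that high-risk outcome rates are biased downward because the worst cases vanish. The documents do not support that. Surgery is the one outcome the protocol names concretely, and a terminated or stillborn fetus has no postnatal surgery. Dropping it removes only a denominator count. The sign turns on a definition of severe course that the protocol does not give. Fetuses that resolve also leave follow-up, by design, which can push observed rates upward.

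**A count of lost outcomes.** The literature review gives "multicystic renal dysplasia (2-5%) and posterior urethral valve (1-5"%. If that valve share held here, it would mean 0.01 x 210 = 2.1 to 0.05 x 280 = 14 valve cases. This shows only that serious urinary causes remain in the eligible pool. A number of lost outcomes also needs the share that ends in termination or death, which no document gives. Nor does any passage show that class A2-3 fetuses leave more often than others.

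**Narrow pool and legitimate target.** Restricting entry to isolated dilation without aneuploidy or other-organ anomalies narrows the pool of terminations and deaths; this stands. Risk in children who reach postnatal care is also a coherent target, but the stated goal concerns fetuses. An analysis plan may settle whether a prenatal loss is an outcome, a competing event or missing, but only if the loss was recorded.

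**Conclusion.** The point holds. Inclusion item 2 and the exclusion of lost patients condition eligibility on events after the second-trimester classification, and the protocol does not provide for recording terminations, fetal deaths, neonatal deaths or births before the control scan. Risk by prenatal class would describe only cases that reach the later examinations.

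The size is unknown. The illustrative shifts rest wholly on assumed loss and outcome rates, and they run in both directions: upward from 30% if urinary-cause deaths and other losses are counted as severe course in sufficient number, downward for surgery alone per fetus identified if the lost fetuses had none. That the sign cannot be determined from the protocol is itself a reason to record these events. The change should be made, but nothing here shows that the study's results would be badly wrong without it.

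**What to change.** Amend the eligibility section and the data collection as follows:

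- Define the cohort by item 1 together with the baseline exclusions: multiple pregnancy, other-organ anomalies and aneuploidy.
- Describe items 2 and 3 as follow-up stages that apply where indicated.
- Replace the exclusion of lost patients with a report of losses by UTD class.
- For every entered fetus, record pregnancy outcome (termination, fetal death, or live birth with gestational week) and neonatal death.
- Report these by UTD class next to the surgery risk, and state whether each is treated as an outcome, a competing event or missing.
- Keep children born before the control scan in the analysis with their last prenatal class.

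The cost is the amended wording and about one more field per case. The downside is that a few cases will have no third-trimester class.
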